9.1.3 Evaluation of Adverse Events

Each AE is evaluated depending on the following categories by the Investigator.

9.1.3.1 Definition of severity of an AE

Wherever possible, all observed AEs will be graded using the CTCAE version 5.0. The severity of the AE shall be classified using the following grading.

Grade 1: Mild; asymptomatic or mild symptoms; clinical or diagnostic observations only; intervention not indicated

Grade 2: Moderate; minimal, local or non-invasive intervention indicated; limiting age-appropriate instrumental activities of daily living (preparing meals, shopping for groceries or clothes, using the telephone, managing money etc.).

Grade 3: Severe or medically significant but not immediately life-threatening; hospitalization or prolongation of hospitalization indicated; disabling; limiting self-care (bathing, dressing and undressing, feeding self, using the toilet, taking medications and not bedridden).

Grade 4: Life-threatening consequences; urgent intervention indicated.

Grade 5: Death related to an AE.

Semicolon (;) indicates "or".

Record the maximum intensity for AE occurring frequently than once a day. If the intensity category changes over a number of days, then those changes should be recorded as a new AE with the onset date of the new intensity.

It is important to distinguish between serious and severe AEs. Severity is a measure of intensity whereas seriousness is defined by the criteria in Section 9.1.1.2. An AE of severe intensity need not necessarily be considered serious. For example, nausea that persists for several hours may be considered severe nausea, but not an SAE. On the other hand, a stroke that results in only a limited degree of disability may be considered a mild stroke but would be an SAE.

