9.1.1.1 Adverse Event

An AE is defined as any untoward medical occurrence in a patient or clinical investigation patient administered a pharmaceutical product and which does not necessarily have a causal relationship with this treatment. An AE can therefore, be any unfavorable and unintended sign, symptom, or disease (including intercurrent illness), deterioration of a pre-existing illness, accident, any suspected drug reaction, or a clinically relevant change of laboratory values temporally associated with the use of a medicinal (investigational) product, whether or not related to the medicinal (investigational) product and/or study treatment.

A treatment-emergent AE (TEAE) will be defined as an AE that begins or worsens in severity after at least one dose of study drug has been administered.

See Section 9.7 below for the instances where a pregnancy should be reported as an AE.

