9.1.2 Recording and Collection of Adverse Events

It is the responsibility of the Investigator to collect all AEs (both serious and non-serious) derived from spontaneous, unsolicited reports of patients, by observation, and by routine open questions.

AE reporting will extend from date of informed consent until completion of the final visit (EOS). Any ongoing AE at EOS visit (Day 360 ± 2 days) should be followed until the outcome is evident and resolved, clinically stabilized or a plausible explanation has been found.

Pre-existing diseases including deranged laboratory values (before participating in the study) are not considered to be AEs, unless the disease worsens during the study period. Concomitant diseases detected during screening or prior to randomization will be recorded in the medical history eCRF.

Signs and symptoms clearly associated with the disease under study (including symptoms of disease progression) should be reported as AEs if they are newly emergent (i.e., findings not previously observed in the patients), or are determined by the Investigator as severe or a worsening, or if the Investigator considers deterioration of disease-related signs and symptoms to be caused directly by the study drug.

Abnormal laboratory values/ ECGs/ vital signs/ ophthalmic/ physical &systemic examination should be reported as AEs only if the Investigator considers the abnormality as clinically relevant or significant or believes that the abnormality should be reported as an AE.

Any dose (and associated symptoms) given to the patient that exceeds the dose prescribed to the patient has, at a minimum, to be recorded as a non-serious AE in the patient file and eCRF. Any case of overdose leading to an AE or SAE should be reported to Medical Monitor according to reporting requirements. In case of an accidental overdose, the patient should be monitored by the Investigator for any adverse clinical events including IOP, as deemed necessary by the Investigator.

After completion of all scheduled visit assessments, the Investigator must document any AEs arising from these assessments. In case of an SAE, the Investigator must also complete an SAE report form and report it to safety contact, as described in Section 9.1.3.3.

All AEs will be recorded in eCRF regardless of the causal relationship to the study drug.

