All AE records should contain AE term/ AE diagnosis, date of onset, severity, relationship to the study drug, outcome, date of recovery or outcome, action taken with respect to study drug, action taken with AE, AE leading to discontinuation of patient from study, and whether the event is classified as serious.

The categorization of action taken with IP, outcome and action taken for AE is described below:

Categories of Actions Taken with IP	Categories of Outcome*	Categories of action taken for AE

 • Dose Delayed • Drug withdrawn temporarily • Drug withdrawn permanently • Unknown • Not applicable 	
 • Recovered/Resolved • Recovered/Resolved with sequelae • Recovering/Resolving • Not Recovered • Fatal • Unknown 	
 • None • Medication • Hospitalization • Non-drug treatment • Patient withdrawn • Other

*If there is more than one AE, only the AE leading to death will be attributed with a fatal outcome.

In cases where multiple symptoms and signs can be described as one diagnosis (disease), the name of the diagnosis is reported as the name of the AE.

For example, running nose, cough, and sore throat: The 3 symptoms can be described as a series of symptoms of "common cold"

⇒ Common Cold or Upper Respiratory Tract Infection

The Investigator must continue to follow-up the patient with all AEs regardless of the causal relationship to the study drug until the AE has resolved or until the condition stabilizes to an acceptable level or is determined to pose no issue, or until follow-up is no longer feasible.

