11.8.1.1 Adverse Events

All AEs will be coded by System Organ Class (SOC) and Preferred Term (PT) according to the Medical Dictionary for Regulatory Activities (MedDRA) version 19.1 or higher. Events will be classified as TEAEs if they start on or after the date of the first dose of study medication. The number of AEs and the number and percentage of patients experiencing AEs will be summarized by severity and relationship to the study medication. SAEs and AEs leading to premature study discontinuation will be summarized. The corresponding listings will be provided. Study drug injection sites will be assessed for injection site reactions/ inflammatory reactions at each study visit.

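### Each between-day change in AE severity, including improvement, becomes a new AE, and no rule joins the records before counting, so the number of AEs counts grade segments and an improving pre-dose AE becomes a TEAE

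*Combined protocol and SAP*

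**What the plan says.** Section 9.1.3.1 has two recording rules for severity.

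- Within a day, one record is kept: "Record the maximum intensity for AE occurring frequently than once a day".
- Across days, a change of intensity opens a new record: "those changes should be recorded as a new AE with the onset date of the new intensity". Nothing limits this to worsening.

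Section 9.1.2 requires every record to stand alone: "All AE records should contain AE term/ AE diagnosis, date of onset, severity, relationship to the study drug, outcome, date of recovery or outcome". Its outcome list offers recovered, recovered with sequelae, recovering, not recovered, fatal and unknown. It does not say which of these applies to a record that ends only because the grade moved. The same section starts AE collection at informed consent, so AEs that precede the first dose will be in the database.

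On analysis, Section 11.8.1.1 states: "The number of AEs and the number and percentage of patients experiencing AEs will be summarized by severity and relationship to the study medication". Treatment-emergent status is set by start date: "Events will be classified as TEAEs if they start on or after the date of the first dose of study medication". The definition in Section 9.1.1.1 is different: "an AE that begins or worsens in severity after at least one dose of study drug has been administered".

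No section links the records of one episode, joins them before counting, or says that a patient is counted once at maximum severity. Section 11.8 leaves detailed safety methods to the SAP, and no separate SAP text on safety is included in the document.

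**The concern.** Safety is a secondary objective (Section 4.2), and the number of AEs by severity and relationship is one of its planned results. A reader will take that number as a count of clinical episodes. Under the recording rule it is a count of periods at constant grade. How far the two differ depends on how often grades move and how closely each of the 75 to 100 planned sites follows them.

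The rule also sits awkwardly beside Section 9.1.2, which merges several symptoms of one illness into a single AE. There the unit is the illness; in Section 9.1.3.1 it becomes the grade.

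Two further effects follow. A patient whose AE changes grade can appear in more than one severity row. And because each new segment has its own onset date, the start-date rule for TEAEs can admit an event that did nothing after dosing except get better.

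**Working it through.** The documents give no AE count or rate, so there is no stated figure to reproduce. The check counts the records that the written rules produce.

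**Step 1: records per episode.** From Section 9.1.3.1, records = 1 + number of between-day grade changes.

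| Grades of one episode, in order | Changes | AE records | Severity rows | If joined at maximum grade |
|---|---|---|---|---|
| 2 | 0 | 1 | 1 | 1 event, grade 2 |
| 1, 2 | 1 | 2 | 2 | 1 event, grade 2 |
| 1, 2, 1 | 2 | 3 | 2 | 1 event, grade 2 |
| 1, 2, 3, 2, 1 | 4 | 5 | 3 | 1 event, grade 3 |

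The number of patients is 1 in every line. Splitting multiplies the event count and spreads the patient over severity rows, but does not change whether the patient had an AE.

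**Step 2: effect on the total.** If a share p of episodes changes grade, with k changes on average in those episodes, the event count is multiplied by 1 + p × k. The documents give neither p nor k, so these values are assumptions for illustration only:

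- p = 0.10, k = 1: 1 + 0.10 = 1.10
- p = 0.10, k = 2: 1 + 0.20 = 1.20
- p = 0.30, k = 1: 1 + 0.30 = 1.30
- p = 0.30, k = 2: 1 + 0.60 = 1.60

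**Step 3: treatment-emergent status.** Set the two TEAE rules side by side for an AE that starts between consent and the first dose.

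| Course after the first dose | Record with post-dose onset? | TEAE by start date (11.8.1.1) | TEAE by definition (9.1.1.1) |
|---|---|---|---|
| Grade unchanged | No | No | No |
| Worsens, 1 to 2 | Yes, the grade 2 record | Yes | Yes |
| Only improves, 2 to 1 | Yes, the grade 1 record | Yes | No |

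The third line is the error. The second line shows that the new onset date also does useful work: it is what allows the start-date rule to capture a pre-dose AE that worsens.

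**Step 4: order of operations.** Suppose an AE were held as one record from onset to resolution, or its records were collapsed before TEAE status was set. The worsening AE in the second line would then keep its pre-dose onset, and the start-date rule would drop it, against Section 9.1.1.1. Status must therefore be set before the records are collapsed.

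**The case against.** The strongest reply is that the protocol defers detailed safety methods to the SAP (Section 11.8), which Section 11.2 says will be final before database lock. A joining rule may appear there. That cannot be excluded. It limits the point to what the written rules imply, and it also means there is a natural place to add the rule.

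A second reply is that the same sentence in Section 11.8.1.1 also gives the number and percentage of patients, and that one recording rule applies to both blinded arms. Both statements are right. They limit the harm, but they do not make the event count a count of episodes.

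A reader might infer more than the text supports:

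- *That false outcomes are forced.* They are not. A segment that improves can be coded as recovering and one that worsens as not recovered, and the date field accepts an outcome date that is not a recovery. What is missing is an instruction on which code to use, so sites may differ.
- *That durations and recovery rates will be distorted.* Section 11.8.1.1 plans no summary of either.
- *That every change of grade opens a new AE.* An AE that recurs within a day is held at its maximum intensity.
- *That long ocular events are hit hardest.* Nothing in the documents shows this, and Section 9.1.4.1 already keeps signs consistent with the natural history of CNV out of AE reporting.

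**Conclusion.** The point holds as a gap between the recording rule and the counting rule. Following Sections 9.1.3.1 and 11.8.1.1 as written, the number of AEs counts grade segments, a patient can appear in several severity rows, and a pre-dose AE that only improves is counted as a TEAE against the definition in Section 9.1.1.1.

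The direction is certain: each between-day change adds one record. The size is not. The factors of 1.10 to 1.60 rest wholly on assumed values and should not be quoted as an estimate for this trial.

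The overall percentage of patients with any AE is not changed by splitting alone. The exception is a summary of TEAEs, where a patient whose only AE was a pre-dose event that improved would be added. It would go too far to infer a biased safety comparison, because the rule does not by itself favour LUBT010 or Lucentis. The primary efficacy analysis and the sample size are untouched. The conclusion assumes that no joining rule exists in a SAP text not included here. The change should be made before database lock.

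**What to change.** Keep the recording rule in Section 9.1.3.1, and add the following to Section 11.8.1.1 or the SAP, in this order:

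1. Link the records of one episode. Set TEAE status on the linked episode as new onset, or worsening in severity, after the first dose. A decrease in severity never creates a TEAE.
2. Then collapse contiguous records with the same term in the same patient (and the same eye for ocular events) into one event at its maximum grade. For an episode that began before dosing, take the maximum over the post-dose records.
3. Count each patient once per term, at maximum severity.
4. Name one outcome code for a segment closed only by a grade change, and take the episode's outcome from its last segment.

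The cost is a small programming task and a link between AE records. Replacing the recording rule with a single record per AE looks simpler, but with the start-date TEAE rule left in place it would lose pre-dose AEs that worsen after dosing.

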9.1.3.2 Relationship to the Study Drug

The assessment of the relationship of an AE to the administration of study drug is based on the presence or absence of a “reasonable possibility” that investigational drug has caused the AE. An AE is considered to be “related” to the study medication if a causal relationship between the IP and an AE is at least a reasonable possibility (i.e., the relationship cannot be ruled out). An AE related to the study drug is referred to as an adverse drug reaction (ADR).

The expression “reasonable causal relationship” is meant to convey that there are facts (evidence) or arguments to suggest a causal relationship (ICH E2A guideline) based on relationship to time of onset and drug administration, temporary withdrawal, not attributable to any other drug or condition, dechallenge and rechallenge information as available.

The causal relationship between an AE and the study drug will be defined as below:

Not Related: When the AE is definitely caused by the patient's clinical state, or the study procedure/ conditions or other concomitant drugs.

Unlikely Related: When the temporal association between the AE and the drug is such that the drug is not likely to have any reasonable association with the AE.

Possibly Related: When the AE follows a reasonable temporal sequence from the time of drug administration but could have been produced by the patient's clinical state or the study procedures/ conditions.

Related: When the AE follows a reasonable temporal sequence from the time of drug administration, abates upon discontinuation of the drug and reappears when the drug is reintroduced.

In final evaluation for reporting, the relationship will be converted into “Binary Determination”. ‘Not Related’ and ‘Unlikely Related’ will be clubbed into “Not Related” and ‘Possibly Related’ and ‘Related’ will be clubbed into “Related” for final reporting purpose.

9.1.3.3 Reporting of Serious Adverse Events

All SAEs occurring after the time of informed consent until the final visit (Day 360 visit) must be reported.

All SAEs should be reported by the Investigator to the Safety Contact via Email (at [contact]) or telephone within 24 hours, regardless of the causal relationship with the IPs (following knowledge of the SAE). After receiving reports of the SAEs, the Safety Contact should communicate with the Investigator to get additional information for evaluation of SAEs.

The Investigator is responsible for reporting SAE (initial report, analyzed report as well as follow-up information) to the Ethics Committee (EC) and/or applicable regulatory authority as per applicable local regulatory requirements of participant countries. All SAEs shall be reported by Investigator/ Sponsor/ Sponsor designee as per applicable regulatory requirements.

The Details of Safety Contact:

[REDACTED]

9.1.3.4 Follow – Up of Serious Adverse Events

The Investigator must continue to follow the patient until the SAE has resolved or until the condition stabilizes to an acceptable level or is determined to pose no issue, or until follow-up is no longer feasible. Any ongoing SAE at EOS visit (Day 360 ± 2 days) should be followed until the outcome is evident and resolved, clinically stabilized or a plausible explanation has been found.

9.1.3.5 Suspected Unexpected Serious Adverse Reactions

An SAE that is also an unexpected ADR is called a Suspected Unexpected Serious Adverse Drug Reaction (SUSAR). Unexpected adverse reactions are adverse reactions, of which the nature, or severity, is not consistent with the recent IB.

Suspected Unexpected Serious Adverse Drug Reactions will be reported in compliance with regulatory reporting requirements of participating countries. The details of reporting of SAE, significant AEs and SUSARs will be captured in the Safety Monitoring Plan (SMP).

9.1.4 Ocular AEs**9.1.4.1 Worsening of Symptoms and Signs of Choroidal Neovascularization**

Worsening of symptoms and signs of CNV should be recorded as an AE or SAE only if judged by the Investigator to have unexpectedly worsened in severity and/or frequency or changed in nature at any time during the study. When recording an unanticipated worsening of CNV, it is important to convey why the development was unexpected. For significant Ophthalmic AEs reportable as SAEs refer the criteria below (Section 9.1.4.2).

Developing symptoms and signs that are consistent with the natural history of CNV secondary to AMD is not considered a reportable adverse event in this study.

For example, moderate loss of visual acuity over time, expansion of the size of the lesion, and increased intraretinal or subretinal fluid are common developments associated with AMD. Such information is recorded in the medical history but are not reportable AEs.

9.1.4.2 Vision Threatening Serious Adverse Events

An AE is considered to be vision-threatening and is a reportable SAE, if it meets one or more of the following criteria:

- Rhegmatogenous retinal detachment or stage 1 to 4 macular holes.
- It requires surgical intervention (e.g., conventional surgery, vitreous tap or biopsy with intravitreal injection of anti-infectives, or laser or retinal cryopexy with gas) to prevent permanent loss of sight.
- Any ophthalmic symptom/ eye disorder other than the above that has sight threatening consequences, requiring urgent intervention e.g. blindness in the affected eye.

9.1.5 Non-Ocular AEs due to VEGF inhibition

9.1.5.1 Arterial Thromboembolic events

Arterial thromboembolic events like myocardial infarction, stroke should be recorded as AEs/SAEs as applicable, as there is a theoretical risk of these events following intravitreal use of VEGF inhibitors.

9.2 Ophthalmic Examination

Ophthalmic examinations will be done on screening and after screening according to the schedule of procedures described in Table 1.

9.3 Physical and Systemic Examination

A physical and systemic examination will be performed at the time of screening and after screening according to the schedule of procedures described in Table 1.

Physical examinations will include, but are not limited to, the below items:

General findings, HEENT exam (head, eyes, ears, nose, and throat), assessment of respiratory, cardiovascular, gastrointestinal, nervous, musculoskeletal, and renal/ urinary systems, lymph nodes, and dermatologic examination (including skin appendages) and other findings/ physical conditions of note. Any abnormal findings will be evaluated for clinical significance.

9.4 Vital Signs

Vital signs, including blood pressure, pulse rate, respiratory rate, and body temperature will be measured at screening and after screening according to the Schedule of Assessment described in Table 1. Any abnormal findings will be evaluated for clinical significance.

9.5 Electrocardiogram Assessments

A 12-lead ECG will be performed at screening and after screening according to the Schedule of Assessment described in Table 1. It will be recorded by qualified personnel after the patient has been resting in the supine position for at least 3 min. Any abnormal findings will be evaluated for clinical significance.

9.6 Clinical Laboratory Examinations

Hematology tests, biochemistry tests including serological test (HIV, HBV, HCV, and syphilis) and urine analysis tests for safety assessment will be performed at screening and after screening according to the Schedule of Assessment described in Table 1.

The list of tests for safety laboratory assessment is shown in Table 4.

Urine Pregnancy test for females of childbearing potential will be performed at Day 1, prior to each dosing, and at EOS. Urine pregnancy test should be performed by the female patients themselves and the results reported to site during the visit.

Serum pregnancy test for females of childbearing potential will be performed at screening. Additional tests may be performed at any time during the trial as determined necessary by the investigator or if required by local regulations.

9.6.1 Central Laboratory Samples

Sample collection and handling for laboratory tests will be conducted in accordance with the laboratory manuals and collected samples will be sent to the central laboratory. Not more than 280 mL of blood per patient will be collected during this study for planned study assessments (until EOS).

Table 4: Clinical Laboratory

Hematology	Biochemistry	Urinalysis	Serology
Hematocrit	Albumin	Routine Examination	HIV
Hemoglobin	Globulin	Color	HBV (HBsAg)
Platelet count	Total protein	Appearance	HCV
Red blood cell count	Alkaline phosphatase	pH	Syphilis (RPR) [#]
White blood cell count	ALT	Urobilinogen	
Differential white blood cell count:	AST	Occult blood	
Neutrophils	Bilirubin (total, Direct & Indirect)	Glucose	
Basophils	BUN	Protein	
Eosinophils	Urea	Ketone	
Lymphocytes	Uric Acid	Specific gravity	
Monocytes	Creatinine		
	Random Glucose	Microscopic Examination	
	Serum pregnancy*	(if abnormality is suspected)	
	FSH**	Red Blood Cells	
		Pus cells	
		Crystals	
		Cast	
		Bacteria	
		Yeast	
		Other	

*Serum pregnancy test will be done in females of childbearing potential.
**Follicle stimulating hormone (FSH) (in all females at screening visit).
Additional confirmatory test may be performed in RPR reactive cases, due to suspected false positivity.
Note: Urine pregnancy test (UPT) to be performed by the female patients themselves and the results reported to site. However, it can be repeated anytime in local/ central laboratory when pregnancy is suspected in any female patient.

Any clinical test results outside the reference value range will be evaluated for clinical significance. After dosing, laboratory abnormalities considered by the Investigator to have worsened compared to that prior to dosing will be recorded as AEs.

